## 6 STUDY OBJECTIVES AND PURPOSE

The primary and secondary objectives of the study are as follows:

Primary Objectives:

- **To assess the physiological effects (both beneficial and deleterious) of the administration of oral arginine in patients with SCD.**

We will initiate a double blinded, placebo controlled phase II trial where SCD patients will receive placebo or a dose of arginine hydrochloride orally for 12 weeks. We will comprehensively assess the physiological effects of arginine administration throughout this clinical trial. These investigations will focus on three target areas— sickle erythrocyte characterization, free radical biology/damage, and endothelial function.

Secondary Objectives:

- **To evaluate the effect of daily oral arginine on clinical vaso-occlusive events in SCD patients.**

Clinical efficacy will be a secondary endpoint of the clinical trial, but patients will be assessed regularly to determine if arginine treatment results in a reduction in clinical VO events or patient reports of pain.

## 7 STUDY DESIGN

### 7.1 Description of Study Design

#### 7.1.1 Description Of Primary And Secondary Endpoints

The primary endpoints for this trial are:

[figure not shown]
- Nitric Oxide (NOx—nitrite+nitrate)
- Sickle Red Blood Cell Gardos Channel Activity
- Sickle Red Cell Density (Advia)

[figure not shown]
The secondary endpoints for this trial are:

- Soluble VCAM
- Nitrotyrosine
- 8-iso-PGF2 $\alpha$
- Ektacytometry
- ET-1
- Fetal hemoglobin (Hb F)
- Echocardiogram
- Measured by emergency room visits, hospitalizations, clinical visits, and pain medication use

### 7.2 Description of Type of Study

The general research design of this proposal is a double blinded, placebo-controlled, Phase II trial of oral arginine in SCD patients. Due to concern over differences in response due to age, two age groups will be tested independently—children under 18 and adults 18 and over. Patients in each age group (children and adult) will be treated with one dose of arginine (0.05 g/kg/day) or placebo divided for BID dosing. Sixteen patients will be randomized to the arginine and placebo arms. Added to this will be the 16 children and 14 adults previously randomized to the high dose arginine arm (0.10 g/kg/day). In total, 94 patients (48 children and 46 adults) will be evaluated as to the effects of arginine.

**Figure 7.1.** Study Design

### 7.2.1 Arginine Administration

Two doses of arginine hydrochloride will be evaluated in this trial; however, for the remaining portion of the trial, randomization will be to only one of those doses (0.05 mg/kg/day). As stated above, patients in each age group (children and adult) will be treated with one dose of arginine (0.05 g/kg/day) or placebo divided for BID dosing. Sixteen patients will be randomized to this dose level and placebo. Patient dose will be calculated according to the patient's weight. The research pharmacist at each institution will distribute a one month's supply of arginine at each clinic visit. Patients and study

personnel will be blinded as to whether the patient is receiving arginine or placebo. At each clinic visit, pill counts will be performed to assess overall compliance with the therapy. Unused medication will be returned to the pharmacy after each clinic visit. Patients will receive arginine for 12 weeks.

### 7.2.2 Patient Monitoring

Patients enrolled in this trial will receive all therapy and monitoring that is considered standard of care for patients with SCD. Patients will be asked about signs and symptoms as they relate to their illness and arginine administration. To assess potential clinical efficacy, study personnel will collect information on emergency room visits and hospitalizations, clinic visits for pain, and pain medication use. This data will be compared with the patient's own history of these events in the 12 months before starting arginine. All clinical information will be collected using standardized study forms. As part of this study patients will have regular blood draws to assess safety and efficacy of arginine. Laboratory monitoring of patients enrolled in the trial will occur as outlined in the table below:

Test	Week -4	Week -2	Study Entry	Week 1	Week 2	Week 4	Week 8	Week 12	Week 14	Week 16
NO—serum	X	X	X	X	X	X	X	X	X	X
Arginine	X	X	X	X	X	X	X	X	X	X
Arginase	X	X	X	X	X	X	X	X	X	X
CBC/retic	X		X	X	X	X	X	X	X	X
Chem panel	X		X	X	X	X	X	X		X
Urinalysis	X		X	X		X		X		X
Met Hb	X		X	X		X	X	X		
βHCG	X	X	X	X	X	X	X	X	X	
Echocardiogram***			X					X		
EKG, CPK isoenzymes and troponin levels #			X	X	X	X	X	X	X	X
Research Labs**	X	X	X	X	X	X	X	X	X	X

\*\* See Laboratory Assessment below for details

\*\*\*The second echocardiogram will be performed at Week 12 only if the first echocardiogram is abnormal at Study Entry.

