## 8 SELECTION AND WITHDRAWAL OF SUBJECTS

### 8.1 Inclusion Criteria

Subjects who meet all of the following criteria are eligible for enrollment into the study:

1. Participant has signed the informed consent.
2. Established diagnosis of Hb SS or S-beta thalassemia
3. History of at least one vaso-occlusive pain events in last 12 months
4. Regular compliance with comprehensive care
5. Aged 5 years or greater
6. Patient is in his/her steady state and not in the midst of any acute complication due to sickle cell disease at enrollment

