### 8.2 Exclusion Criteria

Subjects who meet any of the following criteria are disqualified from enrollment in the study:

1. Inability to take or tolerate oral medications
2. Hepatic dysfunction (SGPT  $\geq$  2X normal and albumin  $\leq$  3.2)
3. Renal dysfunction (Creatinine  $\geq$  1.2 for children and  $\geq$  1.4 for adults)
4. Allergy to arginine
5. Pregnancy
6. Transfusion within the last 90 days
7.  $>$  10 hospital admissions for pain in the last 12 months **or** daily use of opioids and unstable pain (that interferes with work or daily routine) requiring  $>$  3 Hospital Admissions **and**  $>$  10 Emergency Department/Day Hospital visits in the last 12 months
8. Treatment with hydroxyurea within the last 90 days
9. Treatment with any investigational drug in last 90 days
10. Previous evidence of ischemic heart disease or heart failure

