### 9.5.9 Visit Nine

At Visit 9 (Week 14, Study Day  $98 \pm 3$ ), the first follow-up visit, the patient will no longer be on the study drug. The blood drawn for the central lab will not include the Free Radical Tests and the Endothelial Function as in Visits 1, 3, 4, 6, 7, and 8. The blood drawn for the local labs will be enough for the CBC and Reticulocytes tests. Female patients of childbearing potential will receive a pregnancy test. Hospitalization, pain, concomitant medication, and AE information will be collected. For all patients presenting with chest pain or cardiac events, an EKG will be done and CPK isoenzymes and troponin levels will be measured. The discontinuation criteria will be checked to confirm the patient is still eligible for the study.

### 9.5.10 Visit 10

At Visit 10 (Week 16, Study Day  $112 \pm 3$ ), the second follow-up visit, the patient will be seen for the last time. The blood will be drawn and distributed for the central labs in the

same manner that it was collected for Visit 1, 3, 4, 6, 7, 8, and 9. A urinalysis will be performed at this visit. Hospitalization, pain, concomitant medication, and AE information will be collected. For all patients presenting with chest pain or cardiac events, an EKG will be done and CPK isoenzymes and troponin levels will be measured. The discontinuation criteria will be checked to confirm the patient remained eligible throughout the study.

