### *12.4.2 Efficacy*

The goal of this study is to obtain laboratory and clinical information to justify a phase III clinical trial and to provide data to generate accurate power calculations for a subsequent phase III clinical trial. The two age groups (children and adults) will be analyzed separately to assess for differences in response to arginine therapy.

The laboratory variables NO, Gardos Channel activity, sickle red cell density (% of cells >41, as measured by Advia) are of primary interest. Additionally, sVCAM, H3 Technicon, Nitrotyrosine, 8-iso-PGF2 $\alpha$ , Ektacytometry, ET-1, and ECHO will be measured and analyzed as secondary efficacy variables. Since the goal of this protocol is to gain insight into the effect of arginine on multiple physiologic measures (e.g. erythrocyte characterization, endothelial function and free radical biology), we will model the change from baseline for all of the collected measurements over time using random effects longitudinal mixed models, with treatment and baseline measurement as fixed effects. This class of model allows us to control for the correlation induced by having multiple measurements on an individual. We will focus on estimating the relationship between each of the laboratory measures and treatment group over time.

Additionally, by judiciously choosing the structure of the fixed effects over time, we can investigate non-linear dose relationships as well.

Each laboratory measurement will be summarized by age group (pediatric and adult), treatment arm, and measurement time.

Clinical efficacy is a secondary endpoint for this trial. Clinical efficacy data will be collected on all patients. Specifically, patients will be asked for information on emergency room visits and hospitalizations, clinic visits for pain, and pain medication use. All clinical efficacy measurements will be summarized by age group, treatment arm, and measurement time (where applicable). Treatment differences may be examined using appropriate methods as the data permits.

All efficacy data will be analyzed descriptively to provide information for future trials. All analyses will be performed on the intent-to-treat population. Model assumptions will be confirmed and if broken, appropriate methods will be investigated.

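### Section 7.2.2 compares on-study clinical events with each patient's own prior year, in which entry requires a pain event, while the comparison between arms is only optional

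*Protocol*

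**What the plan says.** Section 7.2.2 (Patient Monitoring) lists what is collected to assess potential clinical efficacy: emergency room visits, hospitalisations, clinic visits for pain and pain medication use. It then commits to comparing these data with the patient's "own history of these events in the 12 months before starting arginine".

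Three entry rules bear on that reference year:
- Section 8.1, criterion 3: "History of at least one vaso-occlusive pain events in last 12 months".
- Section 8.1, criterion 6: "Patient is in his/her steady state and not in the midst of any acute complication due to sickle cell disease at enrollment".
- Section 8.2, criterion 7: patients with more than "10 hospital admissions for pain in the last 12 months" are excluded, as are those who meet a second, combined criterion on opioid use, admissions and emergency visits.

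On duration, section 7.2.1 states "Patients will receive arginine for 12 weeks", and the last visit is at week 16 (section 9.5.10).

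Section 12.4.2 (Efficacy) commits to summaries of the clinical measures by age group, treatment arm and measurement time. On comparing arms it says only: "Treatment differences may be examined using appropriate methods as the data permits". It says nothing of the own-history comparison. Section 12.3.3 calls the analyses descriptive, and clinical efficacy is a secondary endpoint.

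**The concern.** The reference period for the comparison is also a period on which patients are selected. A patient who enters because of an event last year has, on average, a prior-year count above his or her own long-run rate. Later counts drift back towards that rate whether or not the drug works. Nothing in the protocol acknowledges or adjusts for this.

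The secondary objective (section 6) asks whether arginine reduces clinical vaso-occlusive events. A before/after fall cannot answer that, because the same fall is expected on placebo. Section 12.1 expects the clinical data to give planning estimates for a phase III trial, so a before/after change taken as an effect size would mislead the next design.

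The two sections also do not agree on which comparison is meant. The one prone to this bias is stated as a commitment, and the one protected by randomisation as an option.

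**Working it through.** **The plan's only clinical-event figure.** Section 12.1 estimates at least 24 events per age group, citing the same prior-year entry criterion. It states no rate or period. At 1 event per patient-year:
- 48 × 12/52 = 11.1 events in 12 weeks.
- 48 × 16/52 = 14.8 events in 16 weeks.
- 24 events need 26 weeks (48 × 26/52), or about 24/11.1 = 2.2 events per patient-year over 12 weeks.

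The figure does not follow from the minimum rate and the stated follow-up, and it supplies no usable rate. The rates below are therefore assumptions.

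**Effect of requiring at least one prior-year event, with no drug effect.** Let N be the prior-year count and m the population rate per year.

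*All patients with the same rate (Poisson).* E[N | N≥1] = m/(1 − e^−m), while the later rate is still m. The apparent fall is 1 − (1 − e^−m) = e^−m.
- m = 1: prior mean 1.58, later rate 1, fall 37%.
- m = 2: prior mean 2.31, later rate 2, fall 14%.
- m = 3: prior mean 3.16, later rate 3, fall 5%.

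*Rates varying between patients (gamma with shape k).* P0 = (k/(k+m))^k, and E[N | N≥1] = m/(1 − P0). Given N, the expected later rate is (k+N)/(k/m + 1). Example with m = 1, k = 1: P0 = 0.5, prior mean 1/0.5 = 2.00, later rate (1 + 2.00)/2 = 1.50, fall 25%.

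For k from 0.5 to 2:

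| Assumed m per year | Fall, N≥1 only | Fall, N from 1 to 10 |
|---|---|---|
| 1 | 19-30% | 19-30% |
| 2 | 9-13% | 7-12% |
| 3 | 5-6% | 2-4% |
| 5 | 2-3% | rise of 3-4% |

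The last column approximates the exclusion of very frequent admissions. It is approximate because the protocol caps admissions and the model caps all events. Both models together give 19-37% at m = 1, 7-14% at m = 2 and 2-6% at m = 3.

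**What each comparison does under no effect.** The simulation used 4,000 trials, 16 versus 16 patients, 12 weeks, k = 1 and entry counts 1-10. For m = 1, 2 and 3:
- Mean within-arm change: −0.49, −0.27 and −0.10 events per year.
- A within-arm t-test declares a significant fall in 19%, 9% and 6% of trials, against a nominal 2.5%. Not all of this excess is due to selection. Subtracting the expected change and repeating the test still gives about 6%, 5% and 5%, because the counts are few and skewed.
- The between-arm difference in change averages about zero, with two-sided rejection of 4-5%.

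**Unequal windows.** At a constant rate, raw counts over 12 weeks are 12/52 = 23% of the prior-year count (77% lower). Over 16 weeks they are 16/52 = 31% (69% lower). Section 7.2.2 does not say that counts are converted to rates.

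**The case against.** The strongest reply is that the sentence sits among data-collection text and that the statistical section governs. Section 12.4.2 firmly promises summaries by arm, the trial has a double-blind placebo group, and any regression to the mean would show there too. Analyses are descriptive, and with 16 patients per arm and few events a reservation about formal comparison is reasonable. This limits the weight of the point. It does not remove the commitment in section 7.2.2, and a summary by arm is not yet a comparison.

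Four stronger readings are tempting, and the documents do not support them:
- *Clinical efficacy is judged only against own history.* Section 12.4.2 presents results by arm and allows a treatment comparison.
- *A fall must appear in every arm.* Its size depends on rates the protocol does not give, and the exclusion of frequent admissions pulls the other way. Near 3 events per year the fall is small, and at 5 it can reverse. The 37% figure needs every patient to have the same rate of 1 per year.
- *The trial's randomised result is biased.* It is not. The selection acts equally on both arms.
- *The before/after change will be the phase III effect size.* Section 12.1 speaks only of planning estimates.

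It is also fair to say that the selecting event (a pain event) is not the same as the listed outcomes. A pain event need not lead to an emergency visit or admission, so the percentages do not carry over directly to any one outcome. A difference in recall is a weak argument, since on-study events are also obtained by asking the patient. Converting counts to rates and the exact count model can be left to the statistical analysis plan.

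**Conclusion.** The point stands as a stated comparison that is badly chosen and not reconciled with the statistical section. Section 7.2.2 commits to a before/after contrast on a period used for selection, and section 12.4.2 leaves the unbiased contrast optional. With no drug effect the apparent fall is about 19-37%, 7-14% and 2-6% at assumed rates of 1, 2 and 3 events per year, with a possible small rise at higher rates. These figures assume Poisson or gamma-Poisson counts, equate the selecting event with the outcome, and approximate the admissions cap. The steady-state criterion may add to the fall and was not modelled. A bias whose size, and even sign, depends on unknown rates makes the own-history change unsuitable as evidence of effect. The comparison of arginine with placebo is unaffected.

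**What to change.** Reconcile sections 7.2.2 and 12.4.2:
- State that the clinical comparison is arginine versus placebo between concurrently randomised arms, within each age group.
- Base it on event rates per follow-up time, with the prior-12-month count as a baseline covariate as the data permit. A Poisson or negative-binomial model with log follow-up time as offset would serve, and the choice can be left to the statistical analysis plan.
- Keep the own-history change, expressed as rates, only as description by arm. Say that it is neither evidence of effect nor the effect size for phase III planning.

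The cost is wording and minor analysis work, since the prior-year history and the on-study events are already collected. With few events the between-arm estimate will be imprecise, and the report should say so.

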# These cardiac enzyme tests need to be done for all subjects who present with chest pain or any event that could be indicative of a cardiac event..

### 7.2.3 Research Laboratory Assessment

Patients will have ongoing assessment for both primary and secondary outcomes throughout the course of the study. Whenever possible, these assessments will be made when the patient is in the steady state and not in the midst of a complication due to sickle cell disease. The schedule for assessing research lab outcomes is outlined in the table below:

Test	Wk -4	Wk -2	Study Entry	Wk 1	Wk 2	Wk 4	Wk 8	Wk 12	Wk 14	Wk 16
Free Radical Biology										
Nitrotyrosine	X	X	X	X	X	X	X	X		X
8-iso-PGF2α	X	X	X	X	X	X	X	X		X
Endothelial Function										
ET-1	X	X	X	X		X	X	X		X
sVCAM-1	X	X	X	X		X	X	X		X
Erythrocyte Characterization										
Advia	X	X	X	X	X	X	X	X	X	X
Ektacytometry	X	X	X	X	X	X	X	X	X	X
Gardos Channel	X	X	X	X	X	X	X	X	X	X
Fetal Hemoglobin	X	X	X			X	X	X		X

## 8 SELECTION AND WITHDRAWAL OF SUBJECTS

### 8.1 Inclusion Criteria

Subjects who meet all of the following criteria are eligible for enrollment into the study:

1. Participant has signed the informed consent.
2. Established diagnosis of Hb SS or S-beta thalassemia
3. History of at least one vaso-occlusive pain events in last 12 months
4. Regular compliance with comprehensive care
5. Aged 5 years or greater
6. Patient is in his/her steady state and not in the midst of any acute complication due to sickle cell disease at enrollment

### 8.2 Exclusion Criteria

Subjects who meet any of the following criteria are disqualified from enrollment in the study:

1. Inability to take or tolerate oral medications
2. Hepatic dysfunction (SGPT  $\geq$  2X normal and albumin  $\leq$  3.2)
3. Renal dysfunction (Creatinine  $\geq$  1.2 for children and  $\geq$  1.4 for adults)
4. Allergy to arginine
5. Pregnancy
6. Transfusion within the last 90 days
7.  $>$  10 hospital admissions for pain in the last 12 months **or** daily use of opioids and unstable pain (that interferes with work or daily routine) requiring  $>$  3 Hospital Admissions **and**  $>$  10 Emergency Department/Day Hospital visits in the last 12 months
8. Treatment with hydroxyurea within the last 90 days
9. Treatment with any investigational drug in last 90 days
10. Previous evidence of ischemic heart disease or heart failure

### 8.3 Subject Discontinuation

Subjects may decide to discontinue participation at any time during the study. Investigators may discontinue any subject at their discretion, if in their professional opinion, the subject's health, safety, and/or well-being is threatened by continued participation in the study. The following circumstances require discontinuation of subjects:

1. Drop in hemoglobin below 5gm/dL
2. Pulmonary failure requiring intubation
3. Hepatic dysfunction (SGPT  $\geq$  3X normal and albumin  $\leq$  3.0)

4. Renal dysfunction (Creatinine  $\geq 1.4$  for children and  $\geq 1.6$  for adults)
5. Focal neurological changes
6. Increase in methemoglobin level to  $> 2X$  normal level
7. Apparent allergic reaction to arginine
8. Severe headache
9. Pregnancy

Adverse events caused by participation in the study may necessitate modifications to the level of participation of a subject or discontinuation of subjects from participation in the study. Subjects who discontinue early from the study will be replaced.

Subjects who discontinue prematurely from the study for any reason will be encouraged to complete the lab evaluations required at Visit 10; these include a urinalysis, the chemistry and hematology panels, central lab evaluations, and completion of the interim health history form. These follow-up evaluations will be conducted as soon as the patient is able to come back in for one follow-up visit.

In the event that a local principal investigator wishes to discontinue a subject at his or her discretion (i.e. not due to one of the criteria listed above) then the investigator must contact the study Principal Investigator, [name], to formalize discontinuation.

[figure not shown]

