### 9.1.2 Dose Modification or Interruption of Study Drug

While oral arginine has been shown to have little toxicity when given in the doses outlined in this study, we will closely monitor signs, symptoms, and laboratory findings to assess for unexpected toxicities. Arginine will be discontinued in any patient who experiences the following:

- Drop in hemoglobin below 5gm/dL
- Pulmonary failure requiring intubation
- Hepatic dysfunction (SGPT  $\geq$  3X normal and albumin  $\leq$  3.0)
- Renal dysfunction (Creatinine  $\geq$  1.4 for children and  $\geq$  1.6 for adults)
- Focal neurological changes
- Increase in methemoglobin level to  $>2X$  normal level
- Apparent allergic reaction to arginine
- Severe headache
- Pregnancy

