### 11.2.9 Subject Discontinuation due to Adverse Event(s)

The following criteria will be used to determine whether or not specific subjects exhibit toxicities of the study drug(s) sufficient to require discontinuation from the study.

While oral arginine has been shown to have little toxicity when given in the doses outlined in this study, we will closely monitor signs, symptoms, and laboratory findings to assess for unexpected toxicities. Arginine will be discontinued in any patient who experiences the following:

- Drop in hemoglobin below 5gm/dL
- Pulmonary failure requiring intubation
- Hepatic dysfunction (SGPT  $\geq 3X$  normal and albumin  $\leq 3.0$ )
- Renal dysfunction (Creatinine  $\geq 1.4$  for children and  $\geq 1.6$  for adults)
- Focal neurological changes
- Increase in methemoglobin level to  $>2X$  normal level
- Apparent allergic reaction to arginine
- Severe headache
- Pregnancy

*In addition, patients will also have arginine discontinued if they become unable to orally ingest arginine or at the request of the patient for any reason. In the event that arginine is stopped, patients will continue to be followed by study personnel to assess for potential side effects of arginine administration.*

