The literature suggests that the average NOx level in stable sickle cell patients is 25.5, with a standard deviation of 2.2. We assume that both groups start out with this mean and that the placebo group maintains this level across the length of the study. Based on preliminary findings, we expect a minimum increase of 1.75 for the high dose in the mean change from baseline NOx and the low dose to have a related 1.375 increase. If we assume that the variance is equivalent for the pre and post measurements, we can calculate the variance of the difference as the sum of the pre and post variances minus twice the covariance between pre and post measurements. Thus, our variance estimate depends greatly on the correlation between the pre and post measurements. Assuming a range of correlations (0.3, 0.5, and 0.7), we can then estimate the sample size we will need to detect the differences of 1.375 and 1.75 at 80% and 90% power. (See table below.)

Total sample sizes (for each age group) by power and correlation for NOx assuming a 1:1:1 randomization.

		Power	
		80%	90%
Correlation	0.7	27	33
	0.5	42	54

	0.3	57	72
--	-----	----	----

Given that the goal of this trial is exploratory, not confirmatory, we do not need to achieve a significant value on any specific hypothesis test. Additionally, a much larger treatment effect is anticipated, potentially giving us more power. Thus, a reasonable sample size to achieve our goals and provide us with a reasonable estimate, with the potential to see a significant effect is in the range of 48 total subjects in each age group. With the elimination of one dose of Arginine, the sample size of 16 adults per remaining treatment group will be used.

Insufficient data is available in the literature at this time to sufficiently estimate the expected within subject variability (at steady state of SCD) for the Gardos Channel Activity and erythrocyte density (MCHC >41) as measured by Advia. Sample size calculations would therefore be based on unfounded assumptions and are therefore not provided.

Since the rate of dropout cannot be estimated at this time, completion of the study will be monitored and dropouts will be replaced as they occur. This should pose no problem due to the relatively short duration of the trial. All available data on dropouts will be used in the analyses.

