## 12.2 Analysis Populations

Patients who receive any clinical trial material (any dose of arginine or placebo) will be included in the intent-to-treat analysis. All analyses will be performed on the intent-to-treat population.

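### Sections 8.3, 9.1.2 and 11.2.9 give the same nine events different consequences, and under 8.3 the scheduled primary laboratory draws after stopping are lost

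*Protocol*

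**What the plan says.** **Section 8.3** introduces nine events with "The following circumstances require discontinuation of subjects". Anyone who discontinues is encouraged, not required, to complete the Visit 10 laboratory evaluations, which include the central laboratory tests. On timing it says: "These follow-up evaluations will be conducted as soon as the patient is able to come back in for one follow-up visit". It also states: "Subjects who discontinue early from the study will be replaced".

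**Section 9.1.2** lists the same nine events under "Arginine will be discontinued in any patient who experiences the following". It says nothing about leaving the study.

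**Section 11.2.9** opens by asking whether subjects "exhibit toxicities of the study drug(s) sufficient to require discontinuation from the study", repeats the nine events, and closes with "In the event that arginine is stopped, patients will continue to be followed by study personnel". The stated purpose of that follow-up is to look for side effects. No visit schedule or efficacy assay is named.

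**Section 12.1** says that "dropouts will be replaced as they occur", and two sentences later that all available dropout data will be analyzed. **Section 12.2** puts everyone who received any study drug into the intent-to-treat set and adds: "All analyses will be performed on the intent-to-treat population". **Section 12.3.5** relies on models that tolerate missing values and makes a comparison of completers with non-completers optional.

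The tables in **7.2.2** and **7.2.3** schedule the three primary measures (NOx, Gardos channel, Advia) at every visit from Week -4 to Week 16.

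**The concern.** A site faced with one of the nine events cannot tell from the protocol whether the patient stops capsules and keeps coming, or leaves the study after at most one visit. Sites may act differently on the same event.

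Following 8.3 costs primary-endpoint data. The loss need not be random with respect to treatment. Section 11.1.1 monitors methemoglobin as a possible harm of raised NO, section 5.6 reports headache with long-term oral arginine, and an apparent allergic reaction to arginine is itself a trigger. The primary objective in section 6 covers harmful as well as beneficial effects, and section 12.4.2 wants the results to justify a phase III trial. Patients who react badly would supply the fewest later laboratory values, and an estimate labeled intent-to-treat would lean towards what happens in patients who remain on drug.

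**Working it through.** **1. The passages side by side**

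| Section | Consequence of the nine events | Follow-up afterwards |
|---|---|---|
| 8.3 | Subject discontinued, then replaced | One encouraged visit, no fixed week |
| 9.1.2 | Arginine stopped | Not stated |
| 11.2.9 | Discontinuation from the study and arginine stopped | Continued, for side effects, no schedule |

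Two further places show that both readings are live. Section 11.2.10 attaches only stopping arginine to a positive pregnancy test. Section 9.5.9 has the discontinuation criteria checked at Visit 9, when every patient is already off drug; at that point they can only decide study status.

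**2. Draws lost under 8.3**

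The post-baseline visits are Weeks 1, 2, 4, 8, 12, 14 and 16, seven in all. A patient who stops just after Week 1 misses six of them (2, 4, 8, 12, 14, 16). One who stops just after Week 4 misses four (8, 12, 14, 16). At most one voluntary draw at an arbitrary time takes their place.

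**3. How far the estimate could move**

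The protocol has no figure to reproduce here: section 12.1 says the dropout rate cannot be estimated. The following are assumptions for illustration. A fraction q of the arginine arm stops, the effect disappears on stopping, and nothing is measured afterwards. The on-drug effect is E = 1.375, the low-dose NOx change in section 12.1; the percentages do not depend on E.

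- Final-visit effect in all treated patients, if all are followed: (1 − q) × E
- Effect expected from those still observed: E
- Overstatement: 1/(1 − q) − 1

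| q | q × 16 patients | (1 − q) × 1.375 | Overstatement |
|---|---|---|---|
| 10% | 1.6 | 1.24 | 1/0.90 − 1 = 11% |
| 15% | 2.4 | 1.17 | 1/0.85 − 1 = 18% |
| 20% | 3.2 | 1.10 | 1/0.80 − 1 = 25% |

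Section 12.4.2 models change over time, so a visit average matters too. If stoppers leave after Week 4, they lose 2 of the 5 on-treatment visits (Weeks 8 and 12). With equal visit weights the overstatement is 1/(1 − 0.4q) − 1:

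- q = 10%: 1/0.96 − 1 = 4%
- q = 15%: 1/0.94 − 1 = 6%
- q = 20%: 1/0.92 − 1 = 9%

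**4. Is replacement the mechanism?**

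A small random-intercept simulation used E = 1.375, SD 2.2, pre-post correlation 0.5, 400 per arm, 6 runs, and stopping in the active arm only. The Week 12 effects were:

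| q | All followed | Cut at stopping | Cut and replaced |
|---|---|---|---|
| 10% | 1.25 | 1.40 | 1.34 |
| 20% | 0.98 | 1.31 | 1.36 |

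Six runs are noisy (the 0.98 should be 1.10 in expectation), so this supports direction only. Cutting data at stopping raises the estimate. Adding replacements shifts it down in one row and up in the other, with no consistent effect.

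**The case against.** The strongest case on the other side has five parts.

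- **No efficacy promise is broken.** A reader might infer that 8.3 breaks a commitment in 11.2.9 to keep collecting the scheduled laboratory measures. It does not: 11.2.9 promises follow-up for side effects only, and 11.2.3 separately requires every adverse event to be followed to resolution or stabilization. This stands. The conflict is about subject status and extent of follow-up.
- **Dropouts are not discarded.** A reader might infer that replacement swaps poor tolerators for good ones. Sections 12.1 and 12.2 do not support that, because treated dropouts and all their available data stay in the analysis. This also stands, but draws never taken are not available data.
- **Harms are still seen.** The triggering event is recorded before the patient leaves, and adverse events are tabulated by arm (12.4.3). This stands for the events themselves, but not for the laboratory course after stopping.
- **The bias is conjectural.** No dropout rate is given, several triggers (hemoglobin below 5 gm/dL, intubation) are disease events that can occur on placebo, pre-stop draws and possibly one later draw remain, and each patient's random intercept uses them. This stands against any statement that the result is biased by a known amount. The risk remains.
- **An on-drug estimate is a legitimate aim in an exploratory trial.** That is fair, but the protocol names intent-to-treat as its analysis, and an on-drug view can be produced from complete data, whereas the reverse is impossible.

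**Conclusion.** The inconsistency is certain and must be reconciled: the same nine events lead to three different statements about who leaves and who is followed. It is also certain that 8.3, if followed, ends the scheduled collection of primary laboratory measures for these patients, and that no analysis plan can restore them.

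That this tilts the result is possible, not shown. The 11 to 25% range for the final visit rests on an assumed 10 to 20% stopping in the arginine arm, complete loss of effect and no data after stopping. The visit-averaged counterpart, for stopping after Week 4, is about 4 to 9%. The direction rests on the same assumptions. It would be too strong to say that the protocol is known to favor patients who tolerate arginine, or that replacement causes the problem. This is a worthwhile, low-cost improvement to a trial that calls its analyses descriptive.

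**What to change.** Reconcile 8.3, 9.1.2 and 11.2.9 so that each event has one stated consequence, and in 8.3 define stopping study drug separately from leaving the study. Then state that:

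- patients who stop drug stay on the existing laboratory and clinical visits through Week 16 unless they withdraw consent;
- those draws, at their scheduled weeks, enter the intent-to-treat analysis;
- replacements are additional to the patients they follow and do not substitute for them.

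No change to the stopping criteria is proposed.

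**Cost.** Amendment wording and a few more draws of a kind already scheduled. With 16 per arm and 10 to 20% stopping, that is about 2 to 3 patients with at most six draws each if they stop after Week 1, so no more than 3 × 6 = 18 per arm in each age group. The statistical downside is that off-drug values dilute the on-drug physiological estimate, which can be reported as a secondary on-treatment analysis.
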